Protocol Title: A Phase II, Open-Label Study of ONC201 in Adults with Recurrent High-Grade

Glioma

Protocol Number: ONC013 (NCT03295396) **Protocol Date:** 19 November 2019 (Version 4.0)

PROTOCOL TITLE: A phase II, open-label study of ONC201 in adults with recurrent high-grade glioma

Protocol Version 04

Date: November 19, 2019

Oncoceutics Study Identifier: ONC013

Overall Principal Investigator:
[name]
Department of Neurology & Herbert Irving Comprehensive Cancer Center
Columbia University Irving Medical Center
[name]
[name]

Sponsor:

Oncoceutics, Inc. [name]

Agent(s): ONC201

IND: 136090

Version 01: 10/19/17

Version 02 (Amendment 1): 04/16/18 Version 03 (Amendment 2): 04/23/18 Version 04 (Amendment 3): 11/19/2019

CONFIDENTIAL

The information contained in this protocol is the confidential property of the Sponsor. It is intended solely for the recipient clinical investigator(s) for the purposes of conducting the clinical protocol and may not be reproduced or disclosed to third parties without proper authorization from the Sponsor.

Study Summary

Title	A phase II, open-label study of ONC201 in adults with recurrent high-grade glioma
Short Title	ONC201 in recurrent high-grade glioma
Oncoceutics Protocol Number	ONC013
IND	136090
Overall Principal Investigator	[name] Department of Neurology & Herbert Irving Comprehensive Cancer Center Columbia University Irving Medical Center
Regulatory Sponsor	Oncoceutics, Inc.
Phase	Phase II
Methodology	Open-label, two arm
Study Duration	Approximately 24 months from start of screening to last subject processed and finishing the study
Objectives	 Primary Objective: To estimate the overall response rate (ORR) by RANO-HGG of ONC201 in adults with recurrent histone H3 K27M mutant glioma Secondary Objectives: To estimate the overall response rate (ORR) by RANO-LGG of ONC201 in adults with recurrent histone H3 K27M mutant glioma Assess the safety, toxicities and tolerability of ONC201 in adults with recurrent high-grade glioma (HGG); Estimate the median progression-free survival (PFS), PFS at 2 and 6 months, overall survival (OS), and median duration of response;
Exploratory Objectives	 Assess the association of ORR with tumor markers including: location (thalamus, brainstem, spinal cord); Histone H3 mutation (H3F3A / H3.3 vs HIST1H3B / H3.1); dopamine receptor D2 (DRD2) and dopamine receptor D5 (DRD5) expression; Assess the association of ORR with circulating markers including: Induction of serum prolactin; early activation of NK cells; immune cytokines and effectors in the serial serum samples by enzyme-linked immunosorbent assay (ELISA);

Number of Subjects	Target enrollment is 95 evaluable subjects for the study. Thirty-nine (39) for Arm A and 56 for Arm B.
Major Inclusion/Exclusion Criteria	Key Inclusion criteria: Histologically confirmed diagnosis of HGG (any histology, including but not limited to glioblastoma, astrocytoma, and oligodendroglioma); presence of histone H3 K27M mutation; unequivocal evidence of progressive disease on contrast-enhanced brain CT or MRI as defined by RANO criteria; measurable disease by RANO-HGG criteria; previous therapy with at least radiotherapy; no more than two prior episodes of recurrence; interval of at least 90 days from the completion of radiotherapy to the first dose of ONC201; age ≥18 years. KPS ≥ 60. Key Exclusion Criteria: Presence of diffuse leptomeningeal disease or evidence of CSF dissemination; tumors with known IDH1 (isocitrate dehydrogenase 1) or known IDH2 mutations
Study Product, Dose, Route, Regimen	ONC201, 625 mg once weekly, oral
Duration of administration	ONC201 treatment will continue if tolerated until disease progression, unacceptable toxicity, or withdrawal of consent, whichever comes first.
Statistical Methodology	Primary Efficacy Analysis: Simon's two-stage design (Simon, 1989) will be used. The null hypothesis that the true response rate is 0.01 will be tested against a one-sided alternative. Arm A In the first stage, 17 patients will be accrued. If there are 0 responses in these 17 patients, the study will be stopped. Otherwise, 22 additional patients will be accrued for a total of 39. Arm B In the first stage of Arm B, 17 patients will be accrued. If there are 0 responses in these 17 patients, the study will be stopped. Otherwise, 39 additional patients will be accrued for a total of 56. At least 3 responses will be required in order for success to be claimed (i.e. for the null hypothesis ($p_0 \le 0.01$) to be rejected in favor of the alternative ($p_1 \ge 0.10$) with 80% power, alpha=0.025). Patients will be analyzed separately in each arm.

TABLE OF CONTENTS

Stu	dy Summary	2
1.	OBJECTIVES	7
1.1	General Study Design	7
1.2	Primary Objective	8
1.3	Secondary Objectives	8
1.4	Exploratory Objectives	8
1.5	Endpoints	8
2.	BACKGROUND	9
2.1	Study Disease	9
2.2	IND Agent	10
2.3	Clinical Studies	18
2.4	Rationale for ONC201 in Glioblastoma and Histone H3 K27M Gliomas	20
2.5	Correlative Studies Background	24
3.	PARTICIPANT SELECTION	25
3.1	Inclusion Criteria	25
3.2	Exclusion Criteria	27
3.3	Inclusion of Women and Minorities	28
4.	REGISTRATION PROCEDURES	28
5.	TREATMENT PLAN	28
5.1	Treatment Regimen	28
5.2	Screening Procedures	29
5.3	Baseline Procedures	30
5.4	On-Treatment Procedures	31
5.5	Efficacy Procedures	32
5.6	End of Treatment Visit	33
5.7	General Concomitant Medication and Supportive Care Guidelines	34
5.8	Criteria for Taking a Participant Off Protocol Therapy	35
5.9	Duration of Follow Up	35
5.10	O Criteria for Taking a Participant Off Study	36
6.	DOSING DELAYS/DOSE MODIFICATIONS	36
7.	ADVERSE EVENTS: LIST AND REPORTING REQUIREMENTS	37

7.1	Reporting of Serious Adverse Events	38
7.2	Adverse Event Characteristics	39
8.	PHARMACEUTICAL INFORMATION	40
8.1	Drug Substance Description	40
8.2	Drug Product Description	41
8.3	Drug Product Supply, Administration and Inventory	42
9.	BIOMARKER, CORRELATIVE, IMAGING SUBMISSION AND SPECIAL STUDIES	43
9.1	Predictive Tumor Biomarker Studies	43
9.2	Circulating Pharmacodynamic Analyses	43
9.3	Immune Cell Studies	44
9.4	ONC201 Plasma Analyses	44
9.5	Imaging submission	44
10	SCHEDULE OF EVENTS	46
11.	MEASUREMENT OF EFFECT	48
11.1	Response Assessment Criteria	48
11.2	Definitions	48
11. 3	B Disease Parameters	48

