1.1 General Study Design

This is an open-label, two arm study. The trial will enroll a total of up to 95 subjects. Arm A will enroll up to a total of 39 evaluable subjects and Arm B will enroll up to a total of 56 evaluable subjects. A Bayesian monitoring approach will be applied to assess safety throughout the trial.

After screening procedures and registration, all subjects will be treated with oral ONC201 (625 mg) once every week. All subjects will remain on study until confirmed progressive disease, unacceptable toxicity, death, withdrawal of consent, or another protocol criterion for subject withdrawal is met, whichever comes first. One treatment cycle will be defined as 28 days (4 weeks), corresponding to 4 doses of ONC201.

Subjects will be evaluated for efficacy approximately every 8 weeks with neuroimaging and clinical evaluation. Neuroimaging studies contrast-enhanced brain MRI or CT for patients unable to undergo MRI) will be performed at baseline and every 8 weeks after treatment initiation. Tumor response will be evaluated by the Response Assessment in Neuro-Oncology (RANO) criteria, both criteria for HGG and low-grade glioma (LGG).

Subjects will be evaluated for safety if they have received any study drug. Toxicity assessments will be continuous during the treatment phase. Adverse events will be monitored throughout the trial and graded in severity according to the guidelines outlined in the NCI Common Terminology Criteria for Adverse Events (CTCAE) version 5.

End of treatment assessments will be performed within 30 days after last drug administration, unless the subject is unable to travel due to deteriorating medical condition. Post-treatment, all participants will be followed until resolution or stabilization of any serious or reportable adverse events occurring during treatment or starting within 30 days of last study drug. Assessments may continue for ongoing reportable adverse events.

Subjects who discontinue study drug must continue to be followed for collection of outcome and/or survival follow-up data until death, withdrawal of permission to record at least survival data, or subject is lost to follow-up. Following the end of treatment assessments, all subjects will be contacted every 30 days (±7 days) to assess for study-treatment related toxicities, initiation of any new anti-cancer treatments, and survival status. Contact may be performed by a site visit, telephone contact, e-mail, fax, or mail.

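### The stage-1 futility rule of each arm stops the study rather than the arm, which conflicts with the separate two-stage design given to each arm

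*Protocol*

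**What the plan says.** The Statistical Methodology row of the protocol's Study Summary states that "Simon's two-stage design (Simon, 1989) will be used", with a null response rate of 0.01, an alternative of 0.10, 80% power and alpha 0.025. It then sets out the arms one after the other.

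- **Arm A:** "In the first stage, 17 patients will be accrued. If there are 0 responses in these 17 patients, the study will be stopped". The alternative is a second stage of 22 more, which brings the arm to 39.
- **Arm B:** "In the first stage of Arm B, 17 patients will be accrued". The consequence of 0/17 is worded as for Arm A, and the alternative is 39 more patients, for a total of 56.
- **Success:** at least 3 responses. This follows the Arm B text, and the row does not say whether it also covers Arm A.
- **Closing sentence:** "Patients will be analyzed separately in each arm".

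Section 1.1 (General Study Design) keeps the arms' sizes apart: "Arm A will enroll up to a total of 39 evaluable subjects and Arm B will enroll up to a total of 56 evaluable subjects". It also describes the trial as a single study with two arms. The Number of Subjects row of the Study Summary likewise gives 95 evaluable subjects as the target for the study, then splits that into 39 and 56. The SAP contains no stopping rule. It presents results by arm and for all patients.

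**The concern.** The consequence of a futile first stage is written at the wrong level. In the protocol's own usage, *the study* is the two-arm, 95-subject trial. Applied to the letter, 0/17 in either arm closes both, including an arm that already has responders. Nothing in the available text says that the other arm continues.

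Two things are at stake. First, the power stated for a stand-alone two-stage design does not hold if another arm's result can end accrual. Second, the trial is open-label and the SAP bases efficacy on investigator-assessed response. If one arm has 0/17 and the rule is unclear, its scope could be settled after the other arm's responses are known. A futility rule should leave no room for that.

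**Working it through.** **Inputs** (Study Summary, Statistical Methodology): n1 = 17 in each arm; stop at 0 responses; N = 39 (Arm A) or 56 (Arm B); success at 3 or more responses; p0 = 0.01; p1 = 0.10. Assumptions of this check: independent arms and exact binomial counts.

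**1. Reproduce the stated Arm B figure.** Success needs at least one response in the first 17 and at least 3 in all 56. Hence

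P(success) = P(X56 ≥ 3) − P(X17 = 0) × P(X39 ≥ 3),

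where X39 counts responses in the 39 second-stage patients.

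- At p = 0.10: 0.9281 − 0.1668 × 0.7622 = 0.9281 − 0.1271 = **0.801**.
- At p = 0.01: 0.0187 − 0.8429 × 0.0070 = **0.0128**, within 0.025.

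The stated 80% is reproduced. A grid search (N up to 60, stage-1 cutoff 0 to 2, success threshold up to 5) finds 17/56 with at least 3 responses to be the design with the smallest expected size under the null at alpha 0.025 and 80% power: 17 + (1 − 0.8429) × 39 = 23.1. Arm B was therefore sized as a stand-alone arm.

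**2. Chance of a futile first stage.** With q = (1 − p)^17 and the same true rate in both arms:

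| True rate | One given arm, q | At least one arm, 1 − (1 − q)² | Both arms, q² |
|---|---|---|---|
| 1% | 84.3% | 97.5% | 71.1% |
| 5% | 41.8% | 66.1% | 17.5% |
| 10% | 16.7% | 30.6% | 2.8% |

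Under arm-level stopping, the whole trial closes at stage 1 only in the last column. Under the literal reading, the third column can trigger closure.

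**3. Arm B power under the literal rule.** The lower bound takes Arm A's stage 1 to read out early enough to stop Arm B, and counts an Arm B closed in this way as not succeeding. It is the stand-alone power times the chance that Arm A has at least one response in 17.

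- Arm A's true rate 10%: 0.801 × (1 − 0.1668) = **66.7%**.
- Arm A's true rate 1%: 0.801 × (1 − 0.8429) = **12.6%**.

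The upper bound takes Arm A to read out after Arm B is complete. Arm B is then untouched, at **80.1%**. The available text gives no accrual order or overlap, so the result is a range: 66.7% to 80.1% with both rates at 10%, and 12.6% to 80.1% if Arm A's rate is 1%.

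**4. Does the same argument apply to Arm A?** With at least 3 of 39 responses, P(success) at p = 0.10 is P(X39 ≥ 3) − P(X17 = 0) × P(X22 ≥ 3) = 0.7622 − 0.1668 × 0.3799 = **69.9%**, even with arm-level stopping. Arm A does not reach 80% on that threshold whichever way the rule is read, so the power argument is confined to Arm B.

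**The case against.** The best answer is that no one running the trial would read the rule literally. Each rule sits under its own arm label. The 17 patients referred to are that arm's own. Each rule is paired with a continuation that enlarges only that arm. The row ends by separating the arms for analysis, and the 80% power matches a stand-alone Arm B. The row is also only a summary. The table of contents lists a Section 13 (Statistical Considerations), but the protocol text available for this point ends within Section 2.2.4.2, so Section 13 may state the rule at arm level.

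Most of this stands as evidence of intent. A reader might infer that the protocol lays down a cross-arm rule under which 0/17 in one arm ends the other. The documents do not support that: no available passage states such a rule, and the context points the other way. A reader might also infer that a closed arm's response-rate objective would go unanswered. That goes too far, because the primary objective is estimation and the SAP analyses every treated patient and reports by arm. A shortened arm would give a less precise estimate and might not complete its test.

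The objection does not remove the conflict. The Arm B paragraph was adapted to its arm in its opening words but not in its consequence, and the consequence is the operative part. Evidence that arm-level stopping was meant is a reason to write it.

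**Conclusion.** Wrong as written, low severity. Both stage-1 rules name the study where the design requires the arm. The likely intent is arm-level stopping, under which Arm B has the power claimed for it.

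If the words were applied literally, with independent arms and both true rates at 10%, Arm B's power would lie between 66.7% and 80.1%, and the chance that at least one arm has 0/17 would be 30.6%, against 16.7% for one arm. If Arm A's true rate were 1%, the worst case for Arm B is 12.6%. The low ends are worst cases that depend on accrual timing. They should not be read as the trial's actual power.

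Nor should a reader infer that rewording would bring Arm A to 80%. Its 69.9% with at least 3 of 39 does not come from this wording, and which threshold and alpha apply to Arm A is a separate question. Section 13 was not available, so this conclusion covers the Study Summary text.

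**What to change.** In both arm paragraphs of the Study Summary's Statistical Methodology row, replace the clause that stops the study with: *accrual to this arm will be stopped; the other arm continues under its own rule*. Check Section 13 and make it agree. If trial-wide stopping is in fact intended, say so explicitly, give the reason, and restate each arm's power under that rule and the expected accrual timing.

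The arm-level correction costs two wording changes, plus a matching edit in Section 13 if needed. It changes no sample size, threshold or analysis, and adds no patients beyond those already planned.

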1. OBJECTIVES

The primary objective of this trial is to determine the efficacy and safety of ONC201, an oral small molecule imipridone DRD2 antagonist, in adult subjects with recurrent HGG.

1.1 General Study Design

This is an open-label, two arm study. The trial will enroll a total of up to 95 subjects. Arm A will enroll up to a total of 39 evaluable subjects and Arm B will enroll up to a total of 56 evaluable subjects. A Bayesian monitoring approach will be applied to assess safety throughout the trial.

After screening procedures and registration, all subjects will be treated with oral ONC201 (625 mg) once every week. All subjects will remain on study until confirmed progressive disease, unacceptable toxicity, death, withdrawal of consent, or another protocol criterion for subject withdrawal is met, whichever comes first. One treatment cycle will be defined as 28 days (4 weeks), corresponding to 4 doses of ONC201.

Subjects will be evaluated for efficacy approximately every 8 weeks with neuroimaging and clinical evaluation. Neuroimaging studies contrast-enhanced brain MRI or CT for patients unable to undergo MRI) will be performed at baseline and every 8 weeks after treatment initiation. Tumor response will be evaluated by the Response Assessment in Neuro-Oncology (RANO) criteria, both criteria for HGG and low-grade glioma (LGG).

Subjects will be evaluated for safety if they have received any study drug. Toxicity assessments will be continuous during the treatment phase. Adverse events will be monitored throughout the trial and graded in severity according to the guidelines outlined in the NCI Common Terminology Criteria for Adverse Events (CTCAE) version 5.

End of treatment assessments will be performed within 30 days after last drug administration, unless the subject is unable to travel due to deteriorating medical condition. Post-treatment, all participants will be followed until resolution or stabilization of any serious or reportable adverse events occurring during treatment or starting within 30 days of last study drug. Assessments may continue for ongoing reportable adverse events.

Subjects who discontinue study drug must continue to be followed for collection of outcome and/or survival follow-up data until death, withdrawal of permission to record at least survival data, or subject is lost to follow-up. Following the end of treatment assessments, all subjects will be contacted every 30 days (±7 days) to assess for study-treatment related toxicities, initiation of any new anti-cancer treatments, and survival status. Contact may be performed by a site visit, telephone contact, e-mail, fax, or mail.

1.2 Primary Objective

• To estimate the overall response rate of ONC201, assessed by RANO-HGG criteria, in adult patients with recurrent histone H3 K27M glioma.

1.3 Secondary Objectives

- Assess ORR. according to RANO-LGG, criteria for non-contrast enhancing lesions.
- Assess the safety, toxicities and tolerability of ONC201 in adults with recurrent high- grade glioma;
- Estimate the median PFS, PFS at 2 and 6 months, median OS, and median duration of response;

1.4 Exploratory Objectives

- Assess the association of ORR with tumor markers including: location (thalamus, brainstem, spinal cord); Histone H3 mutation (*H3F3A* / H3.3 vs *HIST1H3B* / H3.1); DRD2 and DRD5 expression;
- Assess the association of ORR with circulating markers including: Induction of serum prolactin; early activation of NK cells; immune cytokines and effectors in the serial serum samples by ELISA;

1.5 Endpoints

-Efficacy

- Response by RANO-HGG
- Response by RANO-LGG
- Duration of response by either RANO-HGG or RANO-LGG
- Progression free survival by RANO-HGG
- Progression-free survival by RANO-LGG
- Overall survival

-Safety

- Adverse events
- Laboratory evaluations
- KPS status
- Vital signs
- Physical examinations

-Other

- Quality of life Assessment by MDASI Patient Reported Outcomes Questionnaire
- NANO (Neurologic Assessment in Neuro-Oncology)

2. BACKGROUND

2.1 Study Disease

According to the 2007 World Health Organization (WHO) Classification of Tumors of the Central Nervous System (CNS), astrocytoma (a major type of glioma) is classified into grades I, II, III and IV based on histology. Grade I and II astrocytoma are considered low grade glioma (LGG), while grade III (anaplastic astrocytoma) and IV astrocytoma/gliomas as well as Grade III oligodendroglioma are considered HGG. Grade IV glioma, or Glioblastoma Multiforme (GBM), is the most common and lethal primary CNS malignancy and accounts for over 15% of all brain cancers (Patel et al., 2014). The 5-year survival rate for GBM remains at <10% (Stupp et al., 2009). In 2014, there were over 23,300 new cases of cancer involving the brain and nervous system and over 14,000 deaths (Siegel et al., 2014). Although initial treatment typically includes surgery, radiation and chemotherapy, HGG usually recurs less than 6-8 months from initial diagnosis.(Gorlia, et. al. 2012). There are limited choices for treating recurrent disease. Bevacizumab was approved for treating recurrent GBM, but studies repeatedly demonstrated outcomes lacking in overall survival benefit from its use. (Wick, et. al. 2017, Gilbert, et. al. 2014) Thus, recurrent HGG has an unmet clinical need with poor survival and limited treatment options that offer meaningful therapeutic benefit.

In the 2016 edition of WHO classification of CNS tumors, Diffuse Midline Glioma (DMG) with Histone H3 K27M mutant is recognized as a distinct disease entity. Any DMG with the H3 K27M mutation is classified as grade IV (Louis et al, 2016). Histone H3 is one of the proteins that comprise the octameric nucleosome and there are 3 variants: H3.1, H3.2, and H3.3. H3.3 is a replication-dependent H3 variant that represents only a small portion of the total cellular histone H3 pool (Bush et al, 2013). Recently, recurring heterozygous hotspot mutations in *H3F3A* and *H3F3B*, the only two genes in mammals that encode H3.3, were discovered in pediatric and young-adult high-grade astrocytomas. These mutations include K27M (lysine 27 to methionine amino acid substitution), as well as other recurrent amino acid substitutions at positions G34 and K36, of which the predominant mutations include G34R/V and K36M. Although both *H3F3A* and *H3F3B* encode H3.3 with identical amino acid sequences, the H3.3 K36M mutation occurs predominantly in *H3F3B* whereas the other mutations are almost exclusive to *H3F3A* (Behjati et al, 2013).

Different mutations in H3.3 segregate by distinct types of tumors. The K27M mutation is prevalent in pediatric diffuse intrinsic pontine glioma (DIPG) and HGG, primarily restricted to midline locations (spinal cord, thalamus, pons, brainstem) in children and younger adults (Schwartzentruber et al, 2012; Sturm et al, 2012; Fontebasso et al, 2014; Aihara et al, 2014). The G34R/V mutations predominantly associate with pediatric glioblastoma in the cerebral hemispheres (Schwartzentruber et al, 2012). The mechanisms by which histone H3 alterations mediate their oncogenic effects are still poorly understood, although there is some evidence that H3 K27M mutations alter global epigenetic states, including lower overall histone H3 K27M trimethyl (H3K27me3) levels and reduced polycomb repressive complex 2 (PRC2) activity.

The H3K27M mutation may present in patients with leptomeningeal dissemination as

well as tumors not originating from the midline CNS structures. No prospective trials exclusive to histone H3 K27M mutant gliomas have been conducted and therefore prospectively collected outcome data are lacking. However, survival data are well published for DIPG, the vast majority of which contain histone H3.3 or H3.1 K27M mutations (Schwartzentruber et al, 2012; Sturm et al, 2012; Wu et al, 2012). In pediatric DIPG, from the time of diagnosis, median overall survival is 9 months, no chemotherapy has proven efficacy in this disease, and no therapyhas proven effective at progression after radiotherapy (Cohen et al, 2011; Bailey et al, 2013; Rizzo et al, 2015; Chassot et a, 2012). Novel therapies are desperately needed for treatment of H3 K37M mutant gliomas.

